#### 4.2.3.1 Donor Selection

PD-1 R are defined as patients with advanced unresectable stage IIIB/IIIC or metastatic melanoma treated with PD-1 checkpoint inhibitors (either nivolumab or pembrolizumab) who have experienced a durable partial or complete response. Median duration of follow up should be  $\geq 24$  months (for partial responders) or  $\geq 12$  months (for complete responders). Published data indicates that the likelihood of relapse in melanoma patients following this duration of follow up is negligible (Ribas et al. 2016; Robert et al. 2015).

PD-1 R identified as being suitable donors – designated as “PD-1R - donors” - will be separately consented under a donor-specific consent form (see **Appendix: Donor ICF**). PD-1 R donor inclusion and exclusion criteria are enumerated below.

Patients with classical Hodgkin lymphoma (Ansell et al. 2015), gastric cancer (Muro et al. 2016), hepatocellular carcinoma (Feng et al. 2017), head and neck squamous cell carcinoma (Ferris et al. 2016), Merkel cell carcinoma (Kaufman et al. 2016; Nghiem et al. 2016), microsatellite instable (MSI-H) tumors (Le et al. 2015), non-small cell lung cancer (NSCLC) (Gettinger et al. 2015; Garon et al. 2015), renal cell carcinoma (RCC) (Motzer et al. 2015), and urothelial carcinoma (UC) (Balar et al. 2017; Plimack et al. 2017) have all experienced

durable responses to PD-1/PD-L1 therapy. However, the durability of responses in this patient population is unknown. Study investigators will also collect samples from PD-1 R patients with these histologies – designated as “PD-1R– at interest population”.

Inclusion criteria “PD-1R - donors:

1. Documented history of metastatic melanoma (excluding uveal melanoma) treated with pembrolizumab or nivolumab administered singly or in combination.
2. Currently in remission from melanoma with median duration of remission lasting  $\geq 12$  months (for complete responders) or  $\geq 24$  months (for partial responders) measured since initiation of therapy.
3. Willingness to complete donor-specific questionnaire (Appendix 1) to assess exposure to infectious agents including but not limited to SARS-CoV-2.
  - 3.1. Questionnaire (Appendix 1) will include an assessment of whether donor was diagnosed with laboratory-confirmed SARS-CoV-2 infection, experienced symptoms of COVID-19 (e.g., fever, cough, shortness of breath) not explained adequately by another diagnosis, or was exposed to a suspected or confirmed case of COVID-19 or SARS-CoV-2 infection.
4. Willingness to complete donor-specific serologic testing to evaluate infectious agents including SARS-CoV-2.
  - 4.1. To evaluate for the possibility of SARS-CoV-2 exposure and/or infection, all candidate donors will undergo **nasopharyngeal (NP)** and **stool testing** for SARS-CoV-2 using a RT-PCR intended for qualitative detection of SARS-CoV-2 nucleic acids. RT-PCR assay is composed of two principal steps: (1) extraction of nucleic acid from patient NP and stool specimens, (2) one-step reverse transcription and PCR amplification with SARS-CoV-2 specific primers and real-time detection with 2019-nCoV specific probes. Test will be performed by Diagnostic Solutions Laboratory, located at [name].
    - 4.1.1. NP test: DSL COVID-19 NP assay evaluates for the presence of two coronavirus genes, the nucleocapsid and the spike gene. A total of three primer/probe sets were designed to detect nucleocapsid and spike RNA. A total of two primer/probe sets (CDC’s N1 and N3 primers) were designed to detect the viral nucleocapsid gene; 1) N1 is SARS-CoV-19 specific, 2) N3 is a coronavirus generic primer and probe set that can also detect other coronaviruses. The third primer/probe set was designed by Diagnostic Solutions Laboratory using the published SARS-CoV-2 reference genome to detect SARS-CoV-2 specific sequence of the spike gene. Blasting the spike primer and probe set indicated 100% homology with SARS-CoV-2 but no homology with any other nucleotide sequence present in the database, including both SARS-CoV (taxonomy ID 694009) and MERS-CoV (taxonomy ID 1335626). Each primer and probe sets are tested in individual reactions. In addition, the test also detects the human RNase P gene as a sample internal extraction and

amplification control using primers and probe sequences published by CDC. In addition, the test utilizes external controls as described below (low titer positive control and a negative control).

4.1.1.1. A Negative Template Control (NTC) serves as a negative process control to monitor for any reagent contamination and sample carryover that could occur during the extraction and amplification process. The NC consists of elution buffer and is run once for every batch of extracted specimens.

4.1.1.2. A Positive Control (PC) is used to verify that the assay run is performing as intended. The PC is based on genomic RNA from SARS-Related Coronavirus 2 and will be positive for N1, N3, and S. The positive control is used once for each batch of extracted specimens.

4.1.1.3. An Internal Control will be performed on every clinical sample as an endogenous control. The internal control is the human Ribonuclease P (RNase P) gene isolated with the sample RNA of each specimen. It will be used to confirm isolation efficiency as well as amplification.

Interpretation of DSL COVID-19 Assay

Interpretation	RNaseP	SARS-CoV-2 N1	SARS-CoV-2 N3	SARS-CoV-2 spike	Action
COVID Negative	+	-	-	-	Report result
COVID Positive	+	+	+	+	Report result
	+	+	-	+	
	+	+	-	-	
	+	-	-	+	
	+	-	+	+	
	+	+	+	-	
COVID Inconclusive	+	-	+	-	
Repeat testing	-	+/-	+/-	+/-	
*For samples with a repeat inconclusive result, additional confirmatory testing may be conducted, if it is necessary to differentiate between SARS-CoV-2 and SARS-CoV-1 or other Sarbecoviruses currently unknown to infect humans, for epidemiological purposes or clinical management.					

- 4.1.2. Stool test: DSL COVID-19 stool assay evaluates for the presence of three coronavirus genes: SARS-CoV-2 membrane (M), SARS-CoV-2 spike (S) and SARS-CoV-2 nucleocapsid (N). Following adequate detection of RNaseP in a test sample, detection of 1 of the viral genes is sufficient for a positive test result. Due to the discontinuous transcription of all coronaviruses that results in the presence of the capsid gene in a vast majority of the mRNA populations as well as in the full-length viral genome, detection of the capsid gene in the absence of additional genes is expected. The lower limit of detection (LLoD) for each viral gene target was determined by testing serial dilutions of the SARS-CoV-2 genomic isolate in triplicate and is summarized in the DSL COVID-19 validation summary. These data indicate that the LLoD for viral spike (S) and membrane (M) detection is 104 genomic equivalents/mL while the LLoD for viral capsid (N) detection is 103 genomic equivalents/mL. In addition, the observation that the mean CT value for each of the determined LLoDs are very low (close to 40 cycles), it is likely that any signal obtained below a CT of 38 is below the LLoD for the viral target genes and should be disregarded for analytic purposes.
- 4.2. Determination of "SARS-CoV-2 negative" status will be made on nasopharyngeal, blood and stool specimens obtained at two timepoints (every 2 weeks for up to 12 weeks): 1st sample collected at least 14 days before stool sample donation, and a 2nd sample collected at least 14 days after stool sample donation.
- 4.3. As the turnaround of the test is 48-72 hours, the stool sample will be released for FMT use no sooner than 48-72 hours after 2nd test results and donor is deemed "SARS-CoV-2 negative".
- 4.4. Candidate donors with discordant stool and NP SARS-CoV-2 results will be excluded.
- 4.5. Candidate donors excluded based on based on screening and/or testing as described in 3.1 and 4.1.1-4.1.2 above will not be allowed to donate stool specimens for use in this study at this time. This is subject to subsequent revision should stool-specific SARS-CoV-2 testing become available.

Inclusion criteria "PD-1R– at interest population":

1. Documented history of metastatic melanoma (or other malignancies) treated with pembrolizumab or nivolumab or other PD-1/PD-L1 inhibitors.
2. Currently in complete/partial remission with duration of complete/partial remission  $\geq 6$  months since initiation of therapy.

Exclusion criteria:

1. History of suspected/confirmed SARS-CoV-2/COVID infection/exposure.

- 1.1. Any instances of suspected/confirmed SARS-CoV-2/COVID infection/exposure will result in exclusion of candidate donor from further donations and exclusion from clinical use of any FMT manufactured from stool donated by candidate donor beginning 4 weeks prior to the suspected/confirmed SARS-CoV-2/COVID infection/exposure
2. History of antibiotic treatment during the 1 month preceding donation.
3. History of intrinsic gastrointestinal illnesses, including inflammatory bowel disease, irritable bowel syndrome, chronic diarrheal disorder (celiac disease), active primary gastrointestinal malignancies or major gastrointestinal surgical procedures.
4. History of symptomatic autoimmune illness.
5. History of documented chronic pain syndromes (fibromyalgia, chronic fatigue) or neurologic, neurodevelopmental disorders.
6. History of metabolic syndrome, obesity (BMI of >35), or moderate-to-severe malnutrition (as assessed clinically).
7. Documented pregnancy (serum/urine pregnancy test to be performed on women of childbearing potential within 1 week of donation for transplant).

PD-1 R FMT donors will undergo extensive screening including a detailed questionnaire and serological/stool/nasal swab tests (see **Appendices: FMT Donor Screening Questionnaire** and **FMT Donor Lab Testing**) to eliminate possibility of transmitting infectious agents prior to FMT sampling. Only patients deemed suitable by screening questionnaire and serological/stool/nasal swab tests are deemed suitable for FMT donation (see Figure below).

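### The stool SARS-CoV-2 Ct rule for donors is worded backwards: with a detection limit near Ct 40, a signal below Ct 38 is above the limit and should not be ignored

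*Combined protocol and SAP*

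**What the plan says.** All of this is in Section 4.2.3.1 (Donor Selection), in the numbered items of the donor inclusion list.

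- Item 4.1 describes the assay as one-step RT-PCR with real-time detection, for a qualitative result. On who runs it: "Test will be performed by Diagnostic Solutions Laboratory".
- Item 4.1.2 (stool test) gives the positivity rule. Once RNaseP is adequately detected, "detection of 1 of the viral genes is sufficient for a positive test result".
- The same item says the LLoD was found from serial dilutions in triplicate and is "summarized in the DSL COVID-19 validation summary". That summary is not part of the documents.
- On the Ct at the LLoD: "the mean CT value for each of the determined LLoDs are very low (close to 40 cycles").
- The conclusion drawn from that: "it is likely that any signal obtained below a CT of 38 is below the LLoD for the viral target genes and should be disregarded".
- Item 4.2 bases negative status on "nasopharyngeal, blood and stool specimens obtained at two timepoints". Item 4.3 holds release until after the second result.
- Item 4.4: "Candidate donors with discordant stool and NP SARS-CoV-2 results will be excluded".

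Appendix 2 lists SARS-CoV-2 among the stool and nasal tests but gives no Ct cut-off. No other section restates or corrects the Ct sentence.

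**The concern.** The Ct is the cycle at which amplified signal crosses the detection threshold. More starting template means fewer cycles and a lower Ct. If the weakest reliably detectable sample crosses near cycle 40, a sample crossing before cycle 38 holds more virus than that, not less. The sentence draws the opposite conclusion and attaches an instruction to it.

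This is a threshold in a donor safety screen. Applied as written, it would turn a clear stool positive into a result to be ignored. It would also weaken the discordance rule in item 4.4: if the stool signal is set aside, stool reads as negative, agrees with a negative nasopharyngeal (NP) swab, and nothing triggers exclusion. Stool is the material given to recipients, so the test made directly on it should be stated correctly.

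**Working it through.** **Inputs**

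- Mean Ct at the LLoD, from item 4.1.2: close to 40. No exact or per-gene value is given.
- Stated cut-off and direction, from item 4.1.2: signals with Ct below 38 are treated as below the LLoD.
- Assay type, from item 4.1: real-time RT-PCR, so the usual Ct relation applies.
- Amplification efficiency E: not in the documents. The direction needs only E > 0.

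The LLoD concentrations print as 104 and 103 genomic equivalents/mL, probably powers of ten with lost superscripts. They do not enter the check.

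**Relation**

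Template relative to the LLoD = (1 + E)^(Ct at LLoD − Ct of the signal)

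**Direction**

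1. Take any Ct at the LLoD of 38 or higher, which covers 'close to 40', and any signal with Ct below 38.
2. The exponent is then greater than zero.
3. With E > 0 the ratio is greater than 1, so the signal is above the LLoD.

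The plan's inference, that a Ct below 38 puts a signal under the LLoD, is therefore not reproduced for any LLoD Ct in that range. For the inference to hold, the Ct at the LLoD would have to be well under 38, contrary to the value the item gives.

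**One illustration of the literal reading**

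Assume an LLoD Ct between 38 and 40 and E between 0.9 and 1.0, and take a stool signal at Ct 30:

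- lowest case: 1.9^(38 − 30) = 1.9^8 ≈ 170 times the LLoD;
- highest case: 2^(40 − 30) = 2^10 = 1,024 times the LLoD.

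The literal rule would disregard that signal. The multiples depend on the assumptions; the direction does not.

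**Consistency within the item**

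- Positivity rule: one viral gene detected means positive.
- Ct rule, read literally: a gene detected at Ct 30 is disregarded, while one detected at Ct 39 is kept.
- Ct rule with the direction reversed: the weak late signal is disregarded and the strong early one is kept.

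Only the reversed reading is compatible with the positivity rule. The cut-off then simply defines what counts as detected.

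**The case against.** The strongest reply is that the intended meaning can be recovered from the sentence. It calls Ct values near 40 very low, so the writer is using 'low' for weak signal. In that usage, below Ct 38 means weaker than Ct 38, and the conclusion about the LLoD then makes sense. The sentence is also hedged, and it sits in a description of the laboratory's validation work. The outside laboratory runs the assay, and nothing says that site staff receive or act on Ct values. All of this stands. It is why a wording slip is the best explanation and why the point is minor.

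The other screening layers also stand:

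- NP RT-PCR and the two-timepoint rule in item 4.2;
- inclusion item 4 on serology, "Willingness to complete donor-specific serologic testing to evaluate infectious agents including SARS-CoV-2", and the donor selection figure, which rules out donors positive for SARS-CoV-2;
- the questionnaire and the exclusion for suspected or confirmed infection or exposure, with its 4-week look-back on product already made;
- quarantine until results are available.

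The reply does not remove the error. A reader has to override the words to reach the right rule, and no other text supplies it.

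Three stronger readings are tempting, and the documents support none of them:

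- **That the laboratory applies the rule backwards, or that infected product has been released.** Nothing indicates either. Harm would need the laboratory to work against its own validation data. It would also need a donor who sheds virus in stool, is negative on the other specimens at both timepoints, and has no recognised infection or exposure.
- **That 38 is the wrong cut-off even with the direction reversed.** If the LLoD Ct is above 38, a rule of 'above 38' would drop some weak signals that are at or above the LLoD. Whether that happens depends on Ct data in the validation summary, which is not available here. The documents support only a request to confirm the value.
- **That the trial's statistical conclusions are affected.** The sentence has no bearing on the response endpoint or the decision rule.

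**Conclusion.** The point holds as an error of direction in the text. It rests on the standard Ct relation and on an LLoD Ct of at least 38, which the item's own figure supports; no exact LLoD Ct or efficiency is needed. As written, the sentence contradicts the one-gene positivity rule and, if followed, would prevent the discordance exclusion from operating.

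Severity is minor. Confidence is high for the wording error; no consequence in practice has been shown. It still merits correction because it is an uncorrected threshold in a donor-release test. The significance level, power and response-rate analysis in Section 8.5 do not change.

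**What to change.** Replace the Ct sentence in item 4.1.2 with:

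> A stool signal may be disregarded only if its Ct is above the validated cut-off in the DSL COVID-19 validation summary; any viral-gene signal at or below that cut-off, with adequate RNaseP, is a positive result.

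Have the laboratory confirm the cut-off, whether 38 or another value, from its existing data. Swapping 'below' for 'above' corrects the direction but leaves the number unchecked.

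Keep the exclusions in items 4.4 and 4.5 and in the '%' footnote of Appendix 2 as they are.

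The cost is a one-sentence amendment and one query to the laboratory, with no new routine testing. The downside is an occasional lost donation.

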## PD-1 R FMT Donor Selection Criteria

- Metastatic melanoma
- PD-1 treated
- Durable remission  $\geq 12$  (if CR) or  $>24$  (if PR) months

### Seropositive for serious infections

- HIV, hep B, hep C, HTLV-1, HTLV-2, strongyloides, syphilis (blood)
- Multi-drug resistant organisms (MDRO) (VRE, CRE, ESBL)
- SARS-CoV-2

**Not a candidate for FMT donation**

### Seropositive for latent infections

- CMV, EBV, HSV-1/HSV-2, JC virus, HHV-6
- MRSA (nasal swab)

**Potentially a candidate for FMT donation** (if donor/recipient have matching serostatus)

### Other (indeterminate)

- Bacteria (campylobacter, c.difficile, e.coli H7, salmonella, shigella, vibrio, yersinia)
- Viruses (rotavirus, adenovirus, norovirus)
- Fungi/parasites (giardia, cryptosporidium, ova/parasites)

[figure not shown]
**Potentially a candidate for FMT donation** (if repeat studies are negative)

PD-1 R donors will be divided into patients with and patients without liver metastases based on initial staging imaging obtained immediately prior to initiation of PD-1 therapy.

PD-1 R who agree to be donors will donate stool samples which will undergo sample processing and administration as detailed in Section 4.2.3. Serial serological testing will be performed and repeated (see figure below).

- PD-1 R FMT Donors**
- **Durable CR or PR; SARS-CoV-2/COVID 19 exposure/infection excluded**
  - Sample obtained at screening used for serological tests and product (FMT infusate) generation
  - Product (FMT infusate) quarantined till test results including **SARS-CoV-2 available** (D+1 to +16)
  - Product (FMT infusate) released for use (D+16 onwards)
    - Product viability: up to 6 months
    - Serologies repeated: every 2 months

## 4.2.4 Rationale for Endpoints

### 4.2.4.1 Efficacy Endpoints

Primary efficacy endpoint: safety/toxicity and objective response rate (ORR) by RECIST 1.1.

Secondary efficacy endpoints: include incidence of grade III/IV toxicities, safety of FMT administration endoscopically, progression-free survival (PFS), and overall survival (OS).

### 4.2.4.2 Biomarker Research

Biomarker endpoints include:

Analysis of bacterial taxa occurrence (within-sample and between-sample differences) in PD-1 responders, FMT responders and FMT non-responders.

Evaluation of anti-tumor T-cell responses, DC function/maturity by multi-parameter flow cytometry, multiplex immunohistochemistry, analysis of T-cell receptor (TCR) clonality/diversity and genetic mutation/expression studies (RNAseq, exome sequencing).

## 5.0 METHODOLOGY

### 5.1 FMT Recipient Entry Criteria

PD-1 resistant/refractory melanoma (excluding uveal melanoma) as defined as progressive disease (PD) at first (or subsequent) radiographic evaluation that demonstrates disease progression while receiving PD-1 inhibitor treatment. Other eligibility criteria include presence of disease amenable to biopsy and lack of contra-indications to FMT administration.

#### 5.1.1 Subject Inclusion Criteria

A patient must meet all of the following criteria to be eligible to participate in this study:

1. Have a histologically or cytologically confirmed diagnosis of unresectable stage III or IV melanoma. Patient may not have a diagnosis of uveal melanoma.
2. Have received any number of prior systemic therapies for metastatic disease. Prior radiation therapy (any number) and interferon use (any formulation and/or duration) in the adjuvant or metastatic disease settings is permitted. Vaccine therapy will be counted as systemic therapy.
3. **Patient must currently be receiving systemic PD-1 immunotherapy with pembrolizumab or nivolumab to be eligible. Patients who have received PD-1 immunotherapy in the adjuvant setting and then relapsed are eligible.**
4. Must be PD-1 inhibitor refractory/resistant – defined as having received at least 2 doses of pembrolizumab with documented systemic disease progression on staging imaging.
  - a. PD is defined as increase in tumor burden > 20% relative to nadir (minimum recorded tumor burden) by RECIST v1.1.
  - b. Once PD is confirmed, initial date of PD documentation will be considered as the date of disease progression.
  - c. Patients can be enrolled at any time following initiation of PD-1 therapy assuming patients have not had (at any time) a record of response to PD-1 therapy (prior best response of stable disease – acceptable; prior best response of complete/partial response – unacceptable).
  - d. For patients receiving adjuvant PD-1 inhibitor therapy, initial date of PD documentation will be considered as the date of disease progression.
5. Patients with CNS disease (parenchymal but not leptomeningeal) are eligible if CNS metastases are treated and deemed stable (with a repeat CT/MRI imaging study) prior to the enrollment date. If radiation is used to treat CNS parenchymal disease, a 2 week washout period will apply (counted from D1 treatment).

- a. Stability must be confirmed with a repeat CT/MRI imaging study performed as part of the screening evaluation (at least 2 weeks after radiation).
  - b. Patients with new CNS metastases identified during screening are ineligible.
6. Willingness to receive FMT administered endoscopically (colonoscopically) and undergo necessary bowel preparation pre-procedure.
- a. Understand infectious risks associated with FMT administration. Although FMT infusate has been screened for bacteria, viruses, fungi and parasites there is a risk of transmission of known and unknown infectious organisms contained in the donor stool. Post-FMT bacteremia (e.g. E. coli), sepsis and fatal events may rarely occur.
  - b. Understand non-infectious risks associated with FMT administration.
    - i. Possible allergy and/or anaphylaxis to antigens in donor stool.
    - ii. Theoretical risk of developing disease possibly related to donor gut microbiota including but not limited to: obesity, metabolic syndrome, cardiovascular disease, autoimmune conditions, allergic/atopic disorders, neurologic disorders, psychiatric conditions and malignancy.
  - c. Understand risks associated with colonoscopy including risk of infection transmission, colonic perforation, aspiration pneumonia, and death.
  - d. Understand that data regarding the long-term safety risk of FMT are lacking.
7. Amenable to participate in the correlative studies and should have available tumor tissue for tumor biopsies. Acceptable biopsies include surgical biopsy, core biopsy or punch/surgical tumor biopsies (of accessible lesions).
8. Have measurable disease as per RECIST version 1.1. At least 1 of the tumor sites must be amenable to biopsy and this may not be the site of disease used to measure antitumor response.
9. Be willing and able to provide written informed consent for the trial.
10. Be  $\geq 18$  years of age on day of signing informed consent.
11. Have a performance status of 0 or 1 on the ECOG Performance Scale.
12. Demonstrate adequate organ function as defined in **Table 5.1.1**, all screening labs should be performed within 14 days of treatment initiation.

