## 2.0 TRIAL DESIGN

### 2.1 Trial Design

[figure not shown]
This is a phase II Simon two-stage single-center study of concurrent FMT with pembrolizumab in patients with PD-1 resistant/refractory melanoma. The study will be conducted over a 12-week period (and up to 24-weeks in responding patients).

Recipient eligibility is based upon prior exposure to PD-1 inhibitor therapy and response at 1st (or subsequent) restaging scan(s) from week 12 up to week 52. Patients must have received a minimum of 2 cycles to be considered eligible. Patients who have received either nivolumab or pembrolizumab are eligible. Patients who have received pembrolizumab/nivolumab in combination with other investigational agent(s) **may be** eligible at the discretion of the treating investigator. PD-1 refractory disease is defined as progressive disease (PD) at the first (or subsequent) radiographic evaluation while receiving PD-1 inhibitor treatment as assessed by RECIST v1.1 on a restaging scan. Patients with stable disease as their best response are eligible; but patients with complete (or partial) response as their best response are ineligible. Other eligibility criteria include absence of active CNS disease, presence of disease amenable to biopsy and lack of contra-indications to FMT administration. Patients will be stratified on the presence or absence of liver metastases.

Suitable patients will be identified following first (or subsequent) restaging study that documents progressive disease (RECIST v1.1) at any time after a minimum 2 cycles of pembrolizumab or nivolumab up to week 52 (17 cycles of pembrolizumab; 26 cycles of nivolumab). Patients will undergo a screening evaluation consisting of imaging (including CNS if clinically suspected), tumor biopsy, and serological/stool studies to confirm suitability for FMT administration. Eligible patients will receive FMT endoscopically (along with intestinal biopsy) with cycle 1 pembrolizumab (+/- 3 days) followed by 3 further cycles of pembrolizumab (cycles 2-4) following which restaging will be performed. Patients with stable and/or responding disease will continue to receive pembrolizumab on study for 4 cycles. Patients with stable and/or responding disease after 8 cycles of pembrolizumab will continue to receive therapy off study until disease progression or up 2 years from FMT administration (35 cycles total).

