To the best of our knowledge, the evaluation of the role of the gut microbiome in modulating immunological and clinical responses to anti-cancer therapy *in vivo* has been conducted only in syngeneic mice. These studies have significant limitations including the inability of syngeneic murine systems to completely recapitulate the features of spontaneous human tumors and significant differences in intestinal microbiota between mice with identical genetic backgrounds. Given these factors along with the significant greater complexity and inter-individual variability in human microbiota relative to mice, translating these findings to improving outcomes of patients failing PD1/PDL1 blockade is likely to involve more than inoculating non-responders with *Bacteroidales* or *Bifidobacterium*. Under the aegis of a tissue/blood banking protocol (UPCI 96-099) supported by the Skin Cancer SPORE, we have prospectively banked pre-treatment biopsy, pre- and on-treatment blood [serum, processed peripheral blood mononuclear cells (PBMC)] and stool specimens on **PD1Rs** – defined as patients who are alive and demonstrate an ongoing response (complete or partial) at 2 years or greater to pembrolizumab or nivolumab given as standard of care (SOC) therapy for advanced melanoma. As controls, we used patients with non-response to PD-1 monotherapy (**PD1 NR**). This cohort is representative of a “real-world” advanced melanoma population with an overall response rate of 33%. Stool specimens from these **PD1 R** and **PD1 NR** were banked within 4-8 hours at -80°C. In order to minimize variability, stool and oral cavity samples were obtained from age-matched (by decade) and sex-matched PD1Rs and PD1NRs. Prior to sample collection, investigators ensured that patients had not had any recent hospitalizations (within 1 month) and/or receipt of recent antibiotic therapy (within 1 month).

We observed increased relative abundance of *Akkermansia*, *Collinsella* and *Alistipes* species in PD1Rs as compared to PD1NRs (Figure 2), but no differences were observed in the

relative abundance of *Bifidobacterium* species and *Bacteroides fragilis* (data not shown). Because of the limited number of pre-treatment and NR samples, the significance of these findings still needs to be determined with sequential microbiome analysis of larger numbers of PD1Rs and PD1NRs.

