#### **8.5.1.2. Decision Rule:**

Based on prior data on response rates in this patient population, the largest ORR where the proposed treatment would be considered unpromising in this population is 5%. The smallest success proportion that would warrant further subsequent studies with the proposed treatment in this patient population is 25%. The following design is based on Simon's minimax two-stage study design and uses to test the null hypothesis that the true success rate in each patient population is at most 5%.

In Stage 1: Enter 13 evaluable patients and follow for at least 12 weeks. If 0 patients have a confirmed response in this timeframe, we will consider this early evidence that this treatment regimen is not sufficiently active in this patient population. If 1 or more patients have a response, then accrual will continue in the second stage of this trial.

In Stage 2: Enter an additional 7 evaluable patients to the trial. If 2 or fewer successes are observed in the 20 evaluable patients, we will consider this sufficient evidence that this treatment is not sufficiently effective in this patient population. If 3 or more successes are observed in the first 20 evaluable patients, then this treatment will be considered promising in this patient population and will be evaluated further in future studies.

Power and Significance Level: Assuming that the number of successes is binomially distributed, this decision rule has a significance level of 0.07; i.e., there is a 7% chance of finding the drug to be effective when it truly is not. This decision rule has 90% power to detect an effective treatment given that the true response rate is at least 25% using this treatment.

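### The eligibility text is contradictory on relapse after adjuvant PD-1 therapy; if off-drug relapses are enrolled, the 5% null and the stated 7% error need not apply to them

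*Combined protocol and SAP*

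**What the plan says.** **On-drug progression required.** Section 2.1 defines PD-1 refractory disease by progression at a "radiographic evaluation while receiving PD-1 inhibitor treatment as assessed by RECIST v1.1 on a restaging scan". Section 5.1 uses the same idea: an evaluation "that demonstrates disease progression while receiving PD-1 inhibitor treatment". The first sentence of criterion 3 in Section 5.1.1 requires the patient to be on pembrolizumab or nivolumab at the time.

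**Adjuvant sentence.** The second sentence of criterion 3 then states: "Patients who have received PD-1 immunotherapy in the adjuvant setting and then relapsed are eligible". It sets no condition that relapse occurred on drug and no limit on time since the last dose.

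**Criterion 4.** Refractory status is given as at least two pembrolizumab doses plus documented progression on imaging; the on-treatment condition is not repeated. Item 4c excludes patients with a recorded response to PD-1 therapy and sets no upper limit on timing. Item 4d fixes the progression date for patients receiving adjuvant therapy.

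**Decision rule (Section 8.5.1.2).** On the null, "the largest ORR where the proposed treatment would be considered unpromising in this population is 5" percent. On the alternative, "The smallest success proportion that would warrant further subsequent studies with the proposed treatment in this patient population is 25" percent. Stage 1: "Enter 13 evaluable patients and follow for at least 12 weeks"; accrual stops "If 0 patients have a confirmed response in this timeframe". Seven more patients follow, and three or more responses among 20 make the regimen promising. The stated significance level is 0.07 and the stated power 90%. Section 8.5.1.1 makes every eligible, consented patient who began treatment evaluable.

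**The concern.** The primary objective (Section 3.1) is to convert PD-1 non-responders into responders. The trial has no control arm, so the 5% null is its only comparator, and that null is meaningful only for patients in whom PD-1 therapy has been seen to fail.

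A patient who completed or stopped adjuvant PD-1 therapy and relapsed later, off drug, has not been seen to fail it in measurable disease. Item 4c cannot screen such a patient out: adjuvant treatment would normally be given without measurable disease, so there is nothing in which a response could be recorded. If this patient responds on study, pembrolizumab alone may be the reason, yet the response counts in full towards the three that are needed.

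Two screeners could decide differently on the same patient, one applying Section 5.1 and the other the second sentence of criterion 3. With a threshold of three responses, a few such decisions can matter. The plan sets no cap on these patients and no separate analysis of them.

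**Working it through.** **1. Reproduce the stated error.** Inputs from Section 8.5.1.2: n1 = 13, stop at 0 responses, n2 = 7, promising at 3 or more of 20, null rate p = 0.05. With X ~ Bin(13, p) and Y ~ Bin(7, p):

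P(promising) = P(X=1)·P(Y≥2) + P(X=2)·P(Y≥1) + P(X≥3)

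At p = 0.05:
- P(X=1) = 0.3512, P(X=2) = 0.1109, P(X≥3) = 0.0245
- P(Y≥2) = 0.0444, P(Y≥1) = 0.3017
- 0.3512 × 0.0444 + 0.1109 × 0.3017 + 0.0245 = 0.0156 + 0.0335 + 0.0245 = 0.0736

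This agrees with the stated 7% after rounding. At p = 0.25 the same formula gives 0.903, which agrees with the stated 90%.

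**2. Let some patients have a different rate.** Suppose k of the 20 are off-drug adjuvant relapses who respond to pembrolizumab alone at rate q, the other 20 − k respond at 5%, and FMT does nothing. The k patients fall at random into the two stages, so the number in stage 1 is hypergeometric. Given that split, each stage's response count is the sum of two independent binomials, and the rule in step 1 is applied and averaged over the splits. The calculation is exact.

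Both k and q are assumptions; the documents give neither. The range for q runs from 5% (as resistant as the rest) to 33%. The upper value is the only PD-1 response rate of this kind in the protocol; Section 4.2.1 reports it for an "advanced melanoma population with an overall response rate of 33" percent. That is a general cohort, not one of adjuvant relapses.

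| q | k = 1 | k = 2 | k = 4 |
|---|---|---|---|
| 5% | 0.074 | 0.074 | 0.074 |
| 10% | 0.082 | 0.092 | 0.112 |
| 20% | 0.100 | 0.131 | 0.204 |
| 33% | 0.122 | 0.187 | 0.349 |

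Example for k = 2, q = 33%. The chances that 0, 1 or 2 of them fall in stage 1 are 0.1105, 0.4789 and 0.4105; P(promising) given each is 0.1738, 0.1874 and 0.1909. The weighted sum is 0.0192 + 0.0897 + 0.0784 = 0.187.

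**3. What drives the rise.** The average response rate without any FMT effect is [kq + (20 − k) × 0.05]/20. For k = 2, q = 33% it is (0.66 + 0.90)/20 = 0.078; for k = 4, q = 33% it is (1.32 + 0.80)/20 = 0.106. A shift of a few percentage points is enough because the rule needs only three responses.

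**The case against.** The strongest reply is that the protocol, read as a whole, does require on-drug progression. All inclusion criteria must be met together. Criterion 4 requires refractory or resistant disease, and Sections 2.1 and 5.1 define that as progression during treatment. Section 7.1.5.2 starts screening at progression on a restaging scan after two cycles of pembrolizumab or nivolumab. Section 2.1 limits identification to week 52. Item 4d speaks of patients receiving adjuvant therapy, in the present tense, and item 4a measures growth from a recorded nadir, which fits poorly with a patient who had no measurable disease. On this view the adjuvant sentence says only that adjuvant exposure counts as PD-1 exposure.

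Much of this stands. A reader might infer that criterion 3 admits any patient with adjuvant exposure; the documents do not support that, because they are contradictory rather than plainly permissive. The reply does not remove the contradiction, however. A patient progressing during adjuvant PD-1 therapy already satisfies the first sentence of criterion 3, so the second adds something mainly if it covers patients no longer on drug, and criterion 4 does not itself state the on-drug condition.

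A reader might also infer that the trial's false-positive rate is far above 7%. The documents do not support that either. It would need several off-drug relapses with a high response rate to pembrolizumab alone, and neither quantity is given. With two such patients at 10% the rate is 0.09.

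**Conclusion.** The point holds as an inconsistency in eligibility with a conditional effect on the error rate. The 7% is arithmetically correct (0.0736) for a trial in which every patient would respond to pembrolizumab alone at 5%. Whether the 5% null fits everyone enrolled depends on how the second sentence of criterion 3 is applied.

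If no off-drug adjuvant relapses are enrolled, or if they are as resistant as the other patients, nothing changes. Otherwise the rate moves from 0.074 to between 0.09 and 0.19 for two such patients, and to 0.35 for four, with q between 10% and 33% for two and at 33% for four. These figures assume that FMT has no effect, that the remaining patients respond at 5%, and that the off-drug patients are spread at random over the two stages. They show how sensitive the rule is; they do not estimate what this trial will see.

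**What to change.** Reconcile criterion 3, and with it 4 and 4d, with Sections 2.1 and 5.1: state that patients with adjuvant PD-1 exposure are eligible only if RECIST v1.1 progression was documented while they were receiving the PD-1 inhibitor. This uses the protocol's own definition and takes a sentence or two. The cost is a somewhat smaller recruitment pool.

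If off-drug relapses are meant to be eligible, or some are already enrolled:
- Keep the pre-specified 13/20 count and the evaluability rule of Section 8.5.1.1. Removing such patients afterwards would conflict with that rule and would be a post hoc exclusion in an open-label trial, when responses may already be known.
- Report responses separately for on-drug and off-drug progression, as a sensitivity analysis.
- State in Section 8.5.1.2 that the 5% null and the 7% error refer only to patients who progressed on drug.

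This alternative costs one extra table and one sentence. It does not restore the 7% for the pooled count, but it lets a reader see how far a positive result depends on off-drug relapses.
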